- 2. Specific Aim 2: Is there a clinical outcome difference in terms of overall survival after diagnosis within the molecular subclasses of the 54 cases of secondary breast cancers from the childhood cancer survivors and compared to spontaneous breast cancers from the general population cases with the same molecular subclass? We believe the answer to this question will determine if radiation has an independent role in expediting the development of various breast cancers and/or augmenting the biologic lethality of the disease.

If our overriding hypothesis is incorrect, then 2 other potential phenomena may be identified with this data:

- 1. Radiation to the chest during childhood induces a specific type of one of the established molecular subclasses of breast cancer, which may or may not have the same virulence as seen in the general breast cancer population.
- 2. A novel molecular subclass(es), unique to patients with radiation to the chest during childhood, is elucidated. If so, multiple questions can be answered using this data:
 - i. What are the hallmark genes that define this group?
 - ii. What are the patient demographics at time of onset? And
 - iii. What is the expected survival time within this group(s)?

Analysis framework:

Outcome of interest

Primary endpoint:

- The patterns of gene expression and distribution of molecular subtypes of radiation induced breast cancer compared to spontaneous/primary breast cancer

Secondary endpoints:

- Overall survival: Time from diagnosis of breast cancer to death of any cause
- Patient demographics at the time of breast cancer diagnosis.

Subject population:

Inclusion criteria

- 1. Cases: Survivors from the Childhood Cancer Survivor Study Cohort who subsequently developed breast cancer after thoracic radiation, with available breast tissue
- 2. Controls: 1,619 patients with spontaneous primary breast cancers, without previous cancer diagnosis or treatment, obtained from previously published research studies for which the gene expression data is publically available, will comprise the general, spontaneous breast cancer population. The previously published gene expression data is analyzed for subtype composition and is presented in **Figure 2**.¹⁵⁻²²
 - a. All ages
 - b. All stages
 - c. Tumor sample obtained from biopsy or surgical specimen prior to any non-surgical therapy
 - d. Biopsy proven invasive ductal, lobular, mucinous, tubular, colloid or papillary (i.e. epithelial) carcinoma of the breast

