 - e. Primary and secondary breast cancer with any hormone status, including ER+, PR+/-, Her2neu-; ER+,PR+/-, Her2neu +; ER-,PR-, Her2neu-; ER-/PR-, Her2neu +

Exclusion criteria

- 1. Previously published research using gene expression data sets for primary breast cancers previously treated with chemotherapy, hormone therapy, or radiation prior to analysis will not be used for the control population
- 2. Previously published research using gene expression data from cell lines and animal studies will not be used for the control population
- 3. Non-epithelial breast malignancies, including lymphoma or sarcoma of the breast and melanoma and non-melanomatous skin cancers
- 4. In situ carcinomas of the breast

Materials/Data needed from the CCSS

- 1. Adequate secondary breast cancer tissue, from the study patients, to yield sufficient, amplifiable mRNA for eventual hybridization with the Affymetrix U133A Gene Chip.
 - a. N=54 (or more if possible)
 - b. At least five 10-micron scrolls (or equivalent quantity) of tumor tissue, verified by corresponding H&E slide, for each sample
- 2. Clinical data on study patients:
 - a. Age at childhood cancer diagnosis
 - b. Childhood primary tumor diagnosis
 - c. Childhood radiotherapy details (including total body irradiation and pelvic radiotherapy)
 - i. Dose and fractionation to irradiated site

- ii. Radiation dose to the chest
- iii. Age at start of radiation
- d. Age at breast cancer diagnosis
- e. Menopausal status at breast cancer diagnosis
- f. Age at death or last follow-up with current vital status for survival calculations
- g. Use of chemotherapy for treatment of the primary cancer

Statistical and Analytic Plans:

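### Aim 2 draws a conclusion about the lethality of the breast tumour from death of any cause, in two groups whose other deaths can differ in either direction

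*Protocol*

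**What the plan says.** Under Analysis framework, the protocol lists as a secondary endpoint "Overall survival: Time from diagnosis of breast cancer to death of any cause". Specific Aim 2 asks about overall survival after diagnosis, both within the subclasses of the 54 cases and "compared to spontaneous breast cancers from the general population cases with the same molecular subclass". It then states the belief that the answer will settle, among other things, whether radiation has a role in "augmenting the biologic lethality of the disease". The first alternative to the main hypothesis uses similar language: an induced subclass "which may or may not have the same virulence as seen in the general breast cancer population".

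The groups are defined under Inclusion criteria. Cases are "Survivors from the Childhood Cancer Survivor Study Cohort who subsequently developed breast cancer after thoracic radiation". Controls are "1,619 patients with spontaneous primary breast cancers, without previous cancer diagnosis or treatment", drawn from published datasets with no age limit.

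In the list of data needed from the CCSS, the item on deaths (2f) is "Age at death or last follow-up with current vital status for survival calculations". Cause of death is not on the list. Statistical and Analytic Plans names log-rank tests and Cox models for survival. It names no analysis by cause of death and no competing-risk method.

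**The concern.** The endpoint counts every death, while the conclusion concerns only deaths caused by the breast tumour. The two would agree if deaths from other causes were equally frequent in cases and controls. The protocol gives no reason to expect that. By definition the cases carry an earlier cancer and its chest irradiation, and the controls carry neither. Controls of any age may in turn have a substantial death rate of their own from other causes.

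If other deaths are more frequent in cases, survivors would appear to have a more lethal breast cancer when they do not. If they are more frequent in controls, a truly more lethal tumour could be hidden, or a falsely favourable result reported. Aim 2 is one of only two specific aims, and its lethality statement would be read as a biological finding.

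**Working it through.** **No figure of the plan to reproduce.** The protocol gives no number of deaths, effect size or power for Aim 2. Its power statement concerns the subtype comparison. The check therefore sets the endpoint against the inference and illustrates the gap with assumed rates.

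**Inputs from the protocol.** There are 54 cases and 1,619 controls, and about 50% of the radiation-induced cancers are expected to be Luminal A (Specific Aim 1).

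**Assumptions (none is in the protocol).** Hazards are constant. Breast cancer mortality is 2% a year in both groups, so the true breast-cancer-specific hazard ratio is 1. Follow-up is 10 years. Other-cause mortality is varied.

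**Formula.** All-cause HR = (breast hazard + other-cause hazard in cases) / (breast hazard + other-cause hazard in controls).

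| Other-cause, cases | Other-cause, controls | Calculation | All-cause HR |
|---|---|---|---|
| 1% | 0.3% | 0.030 / 0.023 | 1.30 |
| 2% | 0.3% | 0.040 / 0.023 | 1.74 |
| 3% | 0.3% | 0.050 / 0.023 | 2.17 |
| 1% | 1% | 0.030 / 0.030 | 1.00 |
| 1% | 2% | 0.030 / 0.040 | 0.75 |
| 0.5% | 2% | 0.025 / 0.040 | 0.625 |

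The breast tumour is equally lethal in every row. Only the other deaths move the hazard ratio.

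**Sensitivity to the breast cancer rate.** With 4% a year from breast cancer and 0.5% from other causes in controls, other-cause rates of 1, 2 and 3% in cases give 0.050/0.045 = 1.11, 0.060/0.045 = 1.33 and 0.070/0.045 = 1.56. The distortion shrinks as breast cancer mortality rises, but remains.

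**Chance of a false conclusion.** Aim 2 compares within subclass, so the relevant sizes are those of a stratum. Applying the 50% share to both groups, Luminal A has 54 × 0.5 = 27 cases and 1,619 × 0.5 ≈ 810 controls. Log-rank tests were simulated with exponential times, censoring at 10 years, and worse survival declared at z > 1.96. With 2% breast cancer mortality and 0.3% other-cause mortality in controls, the results for 1, 2 and 3% in cases were:

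- Luminal A (27 vs 810): 13–14%, 38–40% and 64–65% (two independent runs).
- Luminal B or Basal (20% each, 11 vs 324): 11, 24 and 41%.
- Her2 (10%, 5 vs 162): 10, 19 and 27%.

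The figures for the two smaller sizes are rougher, because the normal approximation to the log-rank statistic is poor with so few cases.

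**Does anything in the plan repair this?** Comparing within molecular subclass makes the tumours alike, but it does not say what the patients died of. Adjusting for age and stage in a Cox model may narrow the gap in other deaths, but it does not separate causes. The childhood-treatment covariates cannot adjust the case-control comparison, because controls have no such treatment.

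**The case against.** Overall survival is a legitimate endpoint, ascertained without judgement, and is listed as secondary. Aim 2 puts its question in terms of overall survival, and the endpoint answers that question. The overreach lies in one interpretive sentence, introduced as a belief, and in the language of virulence. This stands: the fault is in the inference, and a reader who concluded that the endpoint itself is wrong would go too far.

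A reader might also infer that survivors' other deaths will necessarily pass as breast cancer virulence. The protocol does not support a fixed direction. It gives no death rates, and controls of any age may die of other causes at least as often as the cases, as the last three rows of the table show.

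It is tempting to take the size from a pooled test of all 54 cases against all 1,619 controls. That gives false rates of 19–20%, 59–60% and 88–89% in the first setting, but Aim 2 does not ask the pooled question. The within-subclass rates are lower.

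Finally, the absence of cause of death from the CCSS list does not show that it is unavailable. Breast cancer stage is analysed in the statistical section and is not on that list either, so the list is not exhaustive. It remains true that no stated analysis uses cause of death. This is also not a detail that a later analysis plan would settle, since the protocol itself fixes the endpoint, the inference and the data request, and they do not fit together.

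**Conclusion.** The point holds for the inference. All-cause survival in these two groups cannot determine whether radiation makes the breast tumour more lethal, whichever way the result falls. The bias has unknown sign and size. With breast cancer mortality set equal at 2% a year, the all-cause hazard ratio runs from 0.625 to 2.17 over the other-cause rates tried. The chance of wrongly finding worse survival in a Luminal A-sized stratum is roughly 13 to 65% when the excess of other deaths lies with the cases. These figures rest on assumed constant hazards, 10 years of follow-up, the 50% Luminal A share in both groups and unadjusted tests. They illustrate the problem and do not predict the study's result. The mismatch between endpoint and conclusion does not depend on them. It should be corrected, but it concerns a secondary endpoint and leaves the subtype comparison of Aim 1 untouched.

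**What to change.** 1. Keep overall survival as the endpoint. Reword Aim 2 so that its conclusion is limited to all-cause survival after breast cancer diagnosis. Remove the statement on biologic lethality, and bring the virulence wording in the alternative hypotheses into line.
2. Add cause of death to item 2f of the CCSS data request.
3. Only for control series that also report cause of death, add a within-subclass analysis of breast cancer death with other deaths as competing events, giving cause-specific hazards and cumulative incidence. Any statement on lethality should rest on that analysis alone.

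The first step costs a change of wording and the second one more data item. The third has real costs: fewer events, possible misclassification of cause of death, and a usable control set that may be smaller or even empty, because the controls come from published datasets that the protocol does not say record cause of death. If it is empty, the first step is the whole remedy for the case-control comparison.

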Our overriding hypothesis is that radiation interacts, enhances, and potentially accelerates the individual patient's genetic predisposition to develop breast cancer, but does not fundamentally alter the molecular phenotype. To test this hypothesis, we plan to obtain the 54 (or more if available) formalin-fixed, paraffin-embedded tissue samples of the secondary breast cancer cases from the CCSS bio-repository from women who received thoracic radiation. We plan to subject these samples to RNA extraction, using established protocols that yield expression profiles that are highly concordant with frozen tissue.¹²⁻¹³ This mRNA will then be assayed for quality and quantity and amplified accordingly.¹⁴ The resultant cDNA will then be hybridized, at our core facility, using the Affymetrix U133A gene chip. Using the GeneSpring software platform, gene expression data will then be analyzed using supervised methods (which will query the expression levels of specific, hallmark genes that define the molecular subtypes of breast cancer) as well as unsupervised methods (within the set of 54 cases as well as in conjunction with 1,619 general population cases) to determine the prevalence of known, and potentially novel, molecular subclasses of these secondary tumors. Once the subclass designation is established for the 54 secondary breast cancers, the patient demographics and overall survival time after diagnoses will be compared to their spontaneous/general population

counterparts. Generating this working data will enable us to answer the following clinically important questions, which represent our specific aims:

- Specific Aim 1: What is the prevalence/distribution of Luminal A, Luminal B, Basal, Her2-enriched and breast-like breast cancer subtypes among those women who received thoracic radiation during childhood for their pediatric malignancy versus that observed in the general population of spontaneous breast cancers? Consistent with our overriding hypothesis is that the prevalence of these molecular subtypes will approximate that observed in the general, spontaneous breast cancer population. Therefore, assuming radiation induced breast cancers are representative of the general population, approximately 50% will be Luminal A, 20% will be Luminal B, 20% will be Basal, and 10% will be Her 2+.

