The first layer of analysis will consist of determining the distribution of the molecular subtypes of the secondary breast cancers. The RNA will be isolated from the study samples and in a manner similar to the clustering analysis of the control population, the gene expression status of the 249 genes that define the molecular subclasses will be performed in an unsupervised manner on the 54 study and 1,619 control cases together. To account for batch-effect and paraffin extraction, log-transformation and normalization using the RMA method will be performed, again using GeneSpring software, with all cases included. Genes will undergo an independent QA process (to determine if there is signal susceptibility to the formalin fixation and parafinization process) and will be excluded from the final clustering analysis. The placement of the study cases within the cluster groups, as defined predominantly by the control population, will determine the subclass assignment. A chi-square test will be used to compare the distribution of molecular subtypes between the primary and secondary breast cancers.

The raw data from the .cel files of the study population will also be compared. This will be especially important in the event of the formation of a separate clustering group by the radiation-induced cases and a novel subtype is identified. From this analysis, the genes that define this new subclass will be identified and reported. This approach will also allow the identification of gene expression, unique to previously radiated breast tissue, which spans across all subtypes.

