To study our second aim, the molecular subtype status of the study population will be analyzed as a clinicopathologic factor for it's association with survival as well as with other factors such as age at childhood cancer diagnosis, type of childhood primary malignancy, age at time of radiation for childhood malignancy, radiation dose to the chest during childhood, total radiation dose received during childhood, use of chemotherapy for treatment of childhood malignancy, age and menopausal status at breast cancer diagnosis, and stage at breast cancer diagnosis. Correlative analysis (Spearman's rho, t-tests, ect.) will be used to test for univariable associations between the molecular subtype and the cross-sectional demographic variables. For the time-to-event outcomes such as survival and time to onset of breast cancer the log-rank test will be used to determine univariate associations of the molecular subtype (key risk factor of interest) with these outcomes intervals. Additional risk factors such as age at childhood cancer diagnosis, age at time of radiation for childhood malignancy, and radiation dose to the chest during childhood will also be evaluated similarly. Cox proportional hazards models will be used to evaluate multivariable associations between molecular subtype and each of the time-to-event outcomes, adjusting for other factors found to be significant in univariable analyses, or considered *a priori* to be important to include in the model (e.g. age at diagnosis, breast cancer stage, etc.)

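### The case definition and data request cannot place a tumour inside or outside the radiation field, so they do not support the 'radiation induced' endpoint label or the irradiated-tissue signature

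*Protocol*

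**What the plan says.** **Who is a case.** Under Subject population, Inclusion criteria, the protocol admits "Survivors from the Childhood Cancer Survivor Study Cohort who subsequently developed breast cancer after thoracic radiation, with available breast tissue". The exclusion criteria remove in situ and non-epithelial tumours. No criterion concerns where the tumour lay relative to the field.

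**What the cases are called.** The primary endpoint reads "The patterns of gene expression and distribution of molecular subtypes of radiation induced breast cancer compared to spontaneous/primary breast cancer". The first layer of analysis under Statistical and Analytic Plans says the comparison of raw expression files will allow "identification of gene expression, unique to previously radiated breast tissue, which spans across all subtypes".

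**What Aim 1 asks.** Specific Aim 1 is worded by exposure: it asks about subtypes "among those women who received thoracic radiation during childhood for their pediatric malignancy".

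**What is requested.** Materials/Data needed from the CCSS lists, under childhood radiotherapy details, "Dose and fractionation to irradiated site", "Radiation dose to the chest" and age at the start of radiation. The clinical items also cover ages, primary diagnosis, menopausal status, vital status and chemotherapy. Side, quadrant and field position of the breast tumour are not on the list. Chest dose enters the second-aim analysis as a risk factor. Nowhere is it used to decide whether a tumour arose in irradiated breast.

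**The concern.** Two of the protocol's statements are about irradiated tissue: the endpoint label and the signature. The entry criterion establishes only that the woman's thorax was irradiated. The two coincide if every tumour arose in breast that received dose. They differ if, for example, a woman had one-sided chest treatment and later had cancer in the other breast. The requested data cannot tell these situations apart: even if the irradiated-site item returns the side of the field, there is no tumour side to compare it with.

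The direction matters because the overriding hypothesis is that radiation does not fundamentally change the molecular phenotype, so the expected result is similarity to the general population. If out-of-field tumours are present and look like spontaneous ones, they make the groups more alike. A finding of similarity could then partly reflect exposure misclassification, and the data as requested would not let anyone check.

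**Working it through.** **1. Can the requested data place a tumour?**

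| Needed to call a tumour in-field | Requested? |
|---|---|
| Site irradiated, with dose | Yes |
| Chest dose | Yes |
| Side or borders of the chest field | Not named; may or may not come with the site item |
| Side or quadrant of the breast tumour | No |
| Dose to the affected breast | No |

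The missing tumour location is decisive on its own.

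**2. The plan's own power figure.** The protocol claims more than 80% power for a 2-fold difference with 10 per subtype, a coefficient of variation of 50% and alpha 0.05/10 = 0.005. Read as a comparison of two means (difference 1, common SD 0.5, 10 per group), that gives 95% by the normal approximation and 88% by the t distribution. It concerns differences between subtype groups, not cases against controls, so this point does not rest on it.

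**3. Dilution, as an illustration.** Inputs from the protocol: 54 cases, 1,619 controls, a chi-square test, and a reference mix of Luminal A/Luminal B/Basal/HER2 = 50/20/20/10%. Assumptions of mine: two-sided alpha 0.05, an in-field mix of 30/20/40/10%, an out-of-field share f, and out-of-field tumours with the control mix.

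The case mix is

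p_case = (1 − f) × p_in + f × p_out.

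With p_out = p_control this gives

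p_case − p_control = (1 − f) × (p_in − p_control).

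At f = 20% the Basal share is 0.8 × 40% + 0.2 × 20% = 36%, so the difference is 16 points instead of 20. Simulated power of the 3-df chi-square test (100,000 runs per cell):

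| f | Basal share in cases | Power, all 54 cases | In-field cases, 54 × (1 − f) | Power, in-field only |
|---|---|---|---|---|
| 0 | 40% | 88% | 54 | 88% |
| 10% | 38% | 81% | 49 | 85% |
| 20% | 36% | 70% | 43 | 80% |
| 30% | 34% | 59% | 38 | 75% |

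Under these assumptions the in-field comparison has more power than the all-case one despite fewer cases. The non-centrality scales roughly with n(1 − f)², so holding power in an all-case comparison would need about 54/(1 − f)² cases: 67, 85 and 111 for f = 10, 20 and 30%.

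**4. How far this depends on the assumptions.**

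- Basal doubled to 40% with the other subtypes scaled down (37.5/15/40/7.5%): 81, 73, 63 and 51% for f = 0, 10, 20 and 30%. The pattern is the same.
- A larger in-field shift (20/20/50/10%): 99.8% at f = 0 and 91% at f = 30%. The loss is small.
- In-field 30/20/40/10% but out-of-field tumours at 35/20/35/10% instead of the control mix: 83% at f = 30%, against 59% above. Most of the loss disappears.

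**The case against.** The strongest reply is that the criterion fits the question. Aim 1 and both alternative hypotheses are framed by radiation to the chest, and the protocol uses radiation-induced and secondary breast cancer more or less interchangeably. On that reading the primary comparison needs at most a change of wording. This stands for Aim 1. It does not cover the signature, which is explicitly about irradiated tissue.

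It is also fair that in-field position would not prove that an individual tumour was caused by radiation. It is necessary for the label, not sufficient. And chest dose is analysed as a risk factor, which gives a partial dose-gradient check, though not a match of tumour to field.

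A reader might infer more than the documents support:

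- **That dilution is occurring.** Nothing shows that any of the 54 tumours was out of field, or that any woman had one-sided treatment.
- **That the bias must run towards no difference.** This requires out-of-field tumours to resemble the controls. The cases also differ from controls by a previous childhood cancer and possibly chemotherapy, so their out-of-field tumours need not have the control mix.
- **That the dose analyses are invalid because they list "total radiation dose received during childhood".** This is one candidate factor beside chest dose, and chest dose is the dose variable named for the time-to-event analyses. The protocol does not define total dose as a sum over body sites. Whether to keep it, or to model pelvic dose separately, is a modelling preference and no part of this point.

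**Conclusion.** The point holds in a limited form. The case criterion answers Aim 1 as worded. It does not support the endpoint's radiation-induced label or the signature attributed to irradiated breast tissue, because tumour location is not requested and a tumour therefore cannot be matched to the field. That follows from the text alone.

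The consequence for the subtype comparison is conditional. If a share f of the tumours is out of field and resembles spontaneous cancer, any true difference shrinks by the factor 1 − f, in the direction of the study hypothesis. In the main illustration power goes from 88% to 70% at f = 20% and 59% at f = 30%, but the out-of-field share, the in-field shift and the out-of-field mix are all assumed, and other choices give much smaller losses. This is an inexpensive design improvement. It does not show that the primary comparison is wrong.

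**What to change.** 1. Add to the CCSS request the laterality of the breast tumour, its quadrant where recorded, and the side or field of the chest radiation.
2. Classify each tumour as in-field or as out-of-field/uncertain, by a written rule applied before subtype calls are seen.
3. Keep the all-case comparison as the answer to Aim 1. Add the same chi-square comparison in in-field tumours as a sensitivity analysis.
4. Limit the gene analysis described as specific to irradiated breast tissue to in-field tumours.
5. If location cannot be obtained, reword the endpoint and the signature to refer to breast cancer after thoracic radiation.

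The cost is a few more items in a request that already covers radiotherapy site, dose and fractionation, and fewer cases in the in-field analysis (for instance 43 instead of 54 if a fifth were out of field or uncertain). Rewording alone costs nothing, but leaves the irradiated-tissue question unanswered.

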Figure 1: Molecular subtypes of breast cancer identified. Gene expression profiles of primary breast cancers demonstrating 5 distinct molecular subtypes: luminal A, luminal B, Basal, ERBB2+ (HER2 enriched [ERBB2+]), and normal breast-like. From Perou CM et al. Molecular portraits of human breast tumours. Nature 2000;406:747-52.

Figure 2: Our preliminary data. Supervised clustering analysis using 249 genes identified as hallmark genes in determining the established molecular subtypes applied to 1,619 cases from publicly available U133A-derived .cel files,¹⁵⁻²² after log-transformation and normalization using the RMA method. The approximate subclass designation is noted (scaling precludes detailed dendrogram). Collectively, these cases reflect an adequate, heterogeneous control population. Data obtained from radiation-induced breast cancers will be analyzed within the context of this general population of spontaneous breast cancers.

Special considerations:

The principle investigator has significant experience in extracting RNA and DNA from paraffin-embedded tissues for global profiling analyses.²³⁻²⁵

References:

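### The one clustering the analysis section specifies uses 249 genes chosen to separate the known subtypes, so it cannot show a subclass defined by other genes, and a negative result from it is weak evidence

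*Protocol*

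**What the plan says.** The analysis section of the protocol (Statistical and Analytic Plans) describes a first layer whose purpose is the subtype distribution. The step is applied to "the gene expression status of the 249 genes that define the molecular subclasses" and "will be performed in an unsupervised manner on the 54 study and 1,619 control cases together". Cases are then classified by where they fall: "The placement of the study cases within the cluster groups, as defined predominantly by the control population, will determine the subclass assignment". Genes are screened "to determine if there is signal susceptibility to the formalin fixation and parafinization process", and those that fail are left out of the final clustering. A chi-square test compares the resulting distributions.

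The Figure 2 legend says where the gene list comes from: "Supervised clustering analysis using 249 genes identified as hallmark genes in determining the established molecular subtypes applied to 1,619 cases".

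The specific aims list, as one of two alternatives if the main hypothesis is wrong: "A novel molecular subclass(es), unique to patients with radiation to the chest during childhood, is elucidated". The methods paragraph before the aims separates supervised methods, which query the hallmark genes, from "unsupervised methods (within the set of 54 cases as well as in conjunction with 1,619 general population cases"), and says that both serve to find known and possibly novel subclasses.

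The analysis section adds that the raw .cel data of the study cases will be compared. It says this matters most if the irradiated cases form their own cluster and a novel subtype is identified, and that the step can also find expression unique to irradiated tissue across all subtypes.

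**The concern.** A gene list picked because it separates known classes is a sensible tool for sorting tumours into those classes. It is a poor tool for asking whether a new class exists. If a radiation-related subclass is marked by genes outside the list, the clustering has no information on it. The affected cases go into whichever known subtype they resemble on the 249 genes, and they enter the chi-square comparison under that label.

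This matters because of the direction of the hypothesis. The protocol expects radiation to leave the basic molecular type of the tumour unchanged. A step that cannot see some kinds of change would then be read as agreeing with that expectation.

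**Working it through.** The protocol gives no power or detection probability for a novel subclass, so there is no planned figure to reproduce.

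**1. Passages side by side.**
- The methods paragraph treats hallmark-gene analysis as supervised and lists unsupervised analysis separately, including within the 54 cases.
- The analysis section runs its unsupervised step on the hallmark genes themselves. The Figure 2 legend calls clustering of the controls on the same 249 genes supervised.
- The within-54 analysis does not reappear in the analysis section.
- The .cel comparison has no stated restriction to the 249 genes. Its emphasis, however, is on describing a subclass after a separate cluster has formed. Its other stated use, expression spanning all subtypes, concerns a shared signature and not a subclass.

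**2. Share of cases in the joint clustering.** 54 / (54 + 1,619) = 54 / 1,673 = 3.2%. The groups are therefore set mainly by the controls.

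**3. How much signal the 249 genes might carry.** The documents do not say. Assume 12,000-20,000 genes measured, 300-600 of them marking a novel subclass, and no relation between those markers and the list. Expected overlap = 249 x markers / genes measured:
- 249 x 300 / 20,000 = 3.7
- 249 x 300 / 12,000 = 6.2
- 249 x 600 / 20,000 = 7.5
- 249 x 600 / 12,000 = 12.5

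That is 1.5% to 5% of the list. If radiation acts on the subtype genes themselves, the share would be higher.

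**4. Illustrative simulation.** Ward clustering cut at 5, 6 or 8 groups; known subtypes at 50/20/20/10%. Assumptions not in the protocol: unit-variance noise, subtype gene means from N(0,1), a 2 SD shift in the marker genes, and 10, 20 or 54 novel cases (20 or 54 in the first row). There were 10 runs per setting. A novel group counts as found if at least half its members sit in one cluster and make up at least half of it.

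| Share of the 249 genes shifted, joint clustering with 1,619 controls | Novel group found |
|---|---|
| none (signal only outside the list) | 0% |
| 5% | 0-30% |
| 10% | 40-80% |
| 20% | 50-90% |
| 40% | 40-100% |

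With no biological difference but a residual shift of all study cases (SD per gene 0.25, 0.5, 1.0), a false study-only cluster appeared in 0%, 40% and 70% of runs.

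**5. The 54 cases alone** (40 runs per setting; 10, 20 or 27 novel cases; signal outside the list):
- On the 249 genes: found in 0-10% of runs.
- On the 249 plus 3,000 further genes, 5-10% of the extra genes shifted: found in about 35-100%, depending on group size and tree cut.

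The precision is low. At 40% with 10 runs the standard error is sqrt(0.4 x 0.6 / 10) = 0.15, so these rates show direction only.

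**The case against.** A reader might infer that a novel subclass could almost never appear and that a negative answer is close to built into the plan. The documents do not support that.

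- The plan is not confined to the 249-gene step. The methods paragraph promises unsupervised analysis within the 54 cases, with no 249-gene limit attached, and the analysis section compares the raw .cel data. That comparison is described as especially important if a separate cluster forms, not as conditional on it.
- A 3.2% share does not by itself prevent a separate branch. With about 10% or more of the 249 genes shifted, the novel group often separated despite the 1,619 controls. The protocol itself foresees a separate group.
- The error can run the other way. The cases are paraffin-extracted, while the controls are existing public array data. A residual shift could produce a false novel cluster.
- The gain from a wider gene set depends on the model. In one simulation of 54 cases (15 novel, 1.5 SD shift), adjusted Rand agreement was 0.23-0.30 on the 249 genes and 1.00 on the 2,000 most variable genes. When novel cases also kept a known subtype that affected 1,500 other genes, the figures were 0.15-0.20 and about 0.47. With 20% of the 249 genes shifted, the two gene sets were equal, at about 0.46-0.49.
- The novel subclass is a contingent question and not a numbered aim, and details such as gene filters may be left to a statistical analysis plan that is not shown.

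These points limit the claim but do not remove it. The protocol itself fixes the gene list, the pooling and the assignment rule, and it names a novel subclass as a possible finding. The absence of filter details is not the complaint. The complaint is that the one clustering the analysis section does fix is unsuited to that question.

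**Conclusion.** The point holds in a limited form. The 249-gene joint clustering cannot show a subclass defined only by genes outside the list; this follows from the choice of genes and needs no simulation. A finding of no novel subclass from that step alone is weak support for the main hypothesis.

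How much is lost is not fixed by the documents. If markers fall on the list only by chance (1.5-5% of it under the assumed ranges), detection in the joint clustering is likely to be poor. If about 10% or more of the list is affected, separation is often possible. The point would remain with perfect batch correction, while imperfect correction adds a risk of a false novel group. The methods paragraph and the analysis section should be brought into line, because the analysis that could answer the question is promised in one and not carried into the other.

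**What to change.** 1. Keep the 249 genes for assignment to known subtypes and for the chi-square test.
2. In Statistical and Analytic Plans, carry forward the within-54 unsupervised analysis. State that it uses all genes passing the paraffin check (for example the 2,000 most variable), with resampling-based cluster stability.
3. Check any candidate subclass against the controls before calling it unique to irradiated patients. Clustering within the cases removes the case-control processing offset, but it cannot by itself establish uniqueness.
4. State that the 249-gene clustering alone will not be used to conclude that no novel subclass exists.

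The cost is a change of wording and some computing on arrays already planned. The downside is one more analysis, which must be labelled exploratory. It cannot detect a signature shared by all 54 cases; that remains the task of the case-control comparison.
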